Randomization to Intervention and Control (Delayed Intervention) Arms. Using the randomization module in REDCap and the approach described below, there will be random or minimally biased assignment of subjects to study arms. We will use block randomization with randomly permuted blocks(56) to reduce opportunities for selection bias. The advantage of the permuted block design is that treatment assignment is pre-determined before the trial begins and then assignment remains static throughout the course of the trial(57). Blinding and random assignment will be maintained through continuous supervision by key members of the research team. All staff and participants will be kept blinded to outcome measurements during data collection(58). This technique will maintain complete randomness of the assignment of a subject to a group. Participants will be randomized based on the use of a password protected computer- generated random numbers at baseline to avoid the possibility of study staff subverting randomization as has been noted in previous studies(59). Following completion of the informed assent/consent and baseline assessment, participants will be randomly assigned to one of the two trial arms using the randomization module in REDCap(57). This will minimize the biased assignment of study subjects(60).

Intervention Delivery. If the study participant is randomized to the intervention arm, they will have access to the MyPEEPS Mobile App for the next three months. Participants randomized to the control (delayed intervention) arm will be given access to MyPEEPS Mobile at the 3-month study visit. Through our dashboard, we can monitor when participants login to MyPEEPS Mobile, time spent on each activity, and whether they are actively using the intervention or just logged in. Participants will have 3 months to complete the 4 MyPEEPS Mobile modules, which includes 25 embedded mobile activities (See [Table 3](#)).

Participants in the intervention group will be able to access the MyPEEPS intervention from baseline until the end of month 3 and the control arm (delayed intervention) will have access to the MyPEEPS App from months 4-6 (see [Figure 2](#)). **Overview of data collection time points.** We will conduct simultaneous assessments for both study arms at baseline, 3 months, and 6 months.

Intervention Arm	Baseline		Follow-Up		Follow-Up
	A	XXX	A	XXX	
Delayed Intervention Arm (Control)	A		A	XXX	A
TIMELINE	0 months		3 months		6 months

A =Assessment X =Intervention

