Study Outcomes. The pilot study will be used to assess the preliminary efficacy of MyPEEPS Mobile for YTM. Our primary outcome will be the number of condomless receptive anal and/or vaginal sex acts with either a cisgender male or transgender woman. To estimate the effect size for a larger clinical trial, we will focus on the primary outcome of: Condomless receptive anal or vaginal sex acts. The measures listed in Table 6 have been used in our MyPEEPS trial and piloted with 49 YTM as part of our formative work for this application. We will collect all measures at baseline, 3 and 6 months, other than demographic variables which will only be collected at baseline. We also ask participants to report on their own knowledge of their most recent partners' use of PrEP or ART medications. Given the unreliability of perceptions of partner-related risk in particular(71), we will use these data for a secondary sensitivity analysis (see below). This study is not powered for efficacy or tests of moderation or mediation; nonetheless, the purpose of the inclusion of these factors is to measure the impact of the intervention on

them as intermediate targets given their potential role in behavior change.

Table 6. Outcome Measures

Demographics

Sociodemographic (e.g., age, race/ethnicity level of education, housing status)

Newest Vital Sign(72)

Short Test of Functional Health Literacy (S-TOFHLA)(73)

Transgender Congruence Scale(74)

Measures of Hormone Use

Primary Outcome Measures

Condomless receptive anal and/or vaginal sex (adapted from AIDS-Risk Behavior Assessment)(68-70)

Intermediate Outcome Measures

Self-efficacy for safer sex and situational temptation for unsafe sex(75)

Condom Errors(76)

Health Protective Communication Scale(77)

HIV-Knowledge Questionnaire – HIV-KQ-18(78)

Alcohol and Substance Use(79)

Sexual Behavior Index(80)

Secondary Outcomes

nPEP and PrEP Use

Self-reported HIV and STI Testing

Partner(s) PrEP Use, PrEP Adherence or Viral Suppression (if partner is HIV+)

Program Evaluation

Knowledge of and beliefs about the content of the MyPEEPS Mobile intervention

MyPEEPS intervention acceptability and tolerability(81)

Paradata

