Data Analysis. All multivariate analyses will be preceded by standard descriptive bivariate analyses to describe key variables and relationships among key variables. These analyses will include means, frequency tables, histograms, and examination of distributions. All statistical tests will be two-sided tests with the level of significance at 0.05(60).

Outcomes: This study will examine whether the intervention will reduce the number of condomless receptive anal or vaginal penile sex with either a cisgender male or transgender woman; the primary outcome is a count measure (Table 6 - Outcome Measures). We assume that all count outcome variables follow Poisson or negative binomial (NB) distribution, $y \sim \text{Poi}(\lambda)$ or $y \sim \text{NB}(\lambda, \kappa)$ and all percentage outcomes follow binomial distribution, $y \sim \text{bin}(n, p)$. Let the expected value of outcome, $E(y) = \varphi$, so $\varphi = \lambda$ for count outcomes and $\varphi = p$ for binary outcomes. We propose the following generalized linear mixed model (GLMM) to analyze all outcomes. The level of analysis

will be assessed at each data point. For person i and data assess wave W (i.e. baseline, 3, and 6 months):

$$+ \mu_i,$$

where $h(\cdot)$ is the link function for the GLMM. We will use log-links (Poisson or NB regression) for count

Table 7. Codes for design variables

Months	Intervention			Delayed Intervention		
	Arm	W	INT	Arm	W	INT
Baseline	0	0	0	1	0	0
3 mos	0	1	1	1	1	0
6 mos	0	2	1	1	2	1

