outcomes and logit-links (logistic regression) for binary outcomes. μ_i iid~ $N(0, \sigma^2)$ are personal level random effects for the intercept. Variables Arm, W, and INT are design variables. The codes for the design variables are presented in Table 7. Variable Arm is the indicator for intervention arms (0=intervention arm and 1=delayed intervention arm); variable W is data assess wave indicator (0=baseline, 1=3 months, 2=6 months); and variable INT is the intervention indicator (0=pre-intervention, and 1=post-intervention). COV is a vector of personal level covariates at the baseline, such as age, sex, etc., and $\mathbf{XXXXXXXXXXXXXX}$ is a vector of time-dependent covariates assessed at each wave of data for each subject controlling for potential bias between two arms. This model will include both baseline personal level covariates as well as personal-wave level covariates to control for different types of potential confounders. Regression parameter β_3 is the mean value change for the outcome variables between pre- and post-intervention and measures the impact of the intervention on each outcome variable. For the Poisson or NB models, $\exp(\beta_3)$ is the ratio of mean counts (i.e., risk ratio) between post and pre-intervention. For the logistic models, $\exp(\beta_3)$ is the odds ratio between pre- and post-intervention. If the count outcome has excess 0s (for example, much greater than expected number of people who had 0 receptive condomless anal or vaginal sex act as comparison to number of people who had 1,2,..,etc. number of receptive condomless anal or vaginal sex acts), the above Poisson or negative binomial GLMMs can be extended to zero-inflated Poisson or negative binomial models(82).

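### The model for all outcomes adjusts for unnamed post-randomisation covariates, and the partner PrEP sensitivity rule reads a possible app effect as bias

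*Combined protocol and SAP*

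**What the plan says.** Section 7.6 (Data Analysis Plan for Aim 2) puts a single model forward: "We propose the following generalized linear mixed model (GLMM) to analyze all outcomes". Its terms are Arm, W (wave), INT (0 before and 1 after access to the app, coded in Table 7), a person-level random intercept, a vector of baseline covariates illustrated by age and sex, and a second vector that "is a vector of time-dependent covariates assessed at each wave of data for each subject controlling for potential bias between two arms". Including the second vector is a commitment, not an option: "This model will include both baseline personal level covariates as well as personal-wave level covariates to control for different types of potential confounders". No member of it is named. The plan says that β3, the coefficient of INT, "measures the impact of the intervention on each outcome variable". For count outcomes exp(β3) is a ratio of mean counts.

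The displayed equation is not legible in the text available for review. The point rests on the prose, which describes the wave-level term twice.

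On timing, Section 4.5 states: "Following completion of the informed assent/consent and baseline assessment, participants will be randomly assigned to one of the two trial arms". Section 7.6 adds: "We will collect all measures at baseline, 3 and 6 months, other than demographic variables which will only be collected at baseline". Of the intermediate factors, it says that "the purpose of the inclusion of these factors is to measure the impact of the intervention on" them.

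The Sensitivity Analysis paragraph of Section 7.6 has three steps. Step 1 tests, with the same GLMM, whether partners' PrEP use or HIV status differs before and after the intervention. Step 2 relates those partner factors to condomless anal sex. Step 3 says that a difference in step 1 together with significant effects in step 2 means the estimate of the intervention's effect is biased, and that it will be corrected to a causal one. No estimator is given. Table 6 lists partner PrEP use, adherence and viral suppression as a secondary outcome.

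**The concern.** A covariate value recorded at 3 or 6 months can itself be a result of assignment. Conditioning on it can remove part of the effect that β3 is said to measure. Because the covariates are unnamed and nothing excludes variables the app can change, a reader of exp(β3) cannot tell whether it is the app's total effect or an effect given something the app altered. The choice also stays open until data are seen. Estimating an effect size for a larger trial is a stated purpose of the pilot, so the meaning of the ratio matters even though the pilot is not powered for efficacy.

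The partner-factor rule has the related fault in explicit form. It takes a possible consequence of the intervention as evidence that the randomised estimate is wrong, and then replaces that estimate.

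**Working it through.** **The plan's own figures.** The plan gives no number for this point. The RR of 0.55 in Section 7.6 is a hypothetical pilot result used for a future trial (87% power at n=64, at least 99% at N=320). Those powers cannot be reproduced, because no baseline mean, dispersion or numeric intra-cluster correlation is given. They are mutually consistent: the implied SE at n=64 is 0.598/(1.960+1.126) = 0.194. At N=320 it is 0.194/√5 = 0.087, which gives power above 99.9%. Nothing below depends on them.

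**Timing and need.** Assignment follows the baseline assessment, so of the three waves only the baseline covariate values precede it. Confounding of assignment is removed by randomisation, and chance imbalance at baseline can be handled with baseline covariates. Neither purpose needs 3- or 6-month values.

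**What β3 becomes.** Suppose a fraction f of the log effect passes through an adjusted covariate. The coefficient left on INT is (1−f)·ln(RR). With RR = 0.55 (ln 0.55 = −0.598) and f assumed:

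| f | exp((1−f)·ln 0.55) |
|---|---|
| 0 | 0.55 |
| 0.25 | 0.64 |
| 0.50 | 0.74 |
| 0.75 | 0.86 |

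A simulation on Table 7 coding agrees. It used n=80, 2,000 replicates and a person-conditional Poisson fit. The assumed values were a baseline mean of 5 acts, person SD 0.7 on the log scale, gamma overdispersion 0.8 and a constant effect. Without and with the covariate, the ratios were 0.545 and 0.634 (f=0.25), 0.559 and 0.749 (f=0.50), and 0.550 and 0.862 (f=0.75). With a prognostic covariate that the app cannot affect, both were 0.549.

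**The partner-factor rule.** Step 1 uses the same GLMM. By the plan's own reading of β3, a step 1 difference is therefore an impact of the app on a listed secondary outcome. If that factor also predicts the primary outcome, steps 1 and 2 are both met, yet the total effect from the randomised comparison is unbiased. Chance imbalance or differential attrition could meet them too. The steps contain nothing that separates these explanations.

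A second simulation shows the rule at work. It had 40 per arm, three waves, Poisson counts with an assumed mean of about 4, a log-link GEE standing in for the GLMM, and 400 runs per case. A continuous covariate with no confounding stood in for the partner factor. Steps 1 and 2 were both taken as met at p<0.05, although the plan sets no threshold for step 1.

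| Mediated share | Steps 1 and 2 both met | Ratio without the covariate (true 0.55) |
|---|---|---|
| 0 | 8% | 0.552 |
| 25% | 31% | 0.548 |
| 50% | 78% | 0.544 |

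The rule would have called an essentially unbiased estimate biased in those runs.

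**Outcome mismatch.** Step 2 names anal sex only. Elsewhere Section 7.6 states: "Our primary outcome will be the number of condomless receptive anal and/or vaginal sex acts with either a cisgender male or transgender woman".

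**Precision given up.** In the first simulation, the SD of β3 without and with a covariate the app cannot affect was 0.333 and 0.335, 0.345 and 0.335, and 0.382 and 0.348, for assumed log-rate coefficients of 0, 0.2 and 0.4 per SD. That is no material change, then 0.345/0.335 = 1.03 and 0.382/0.348 = 1.10. At n=64 (80% retention) the largest ratio was 0.421/0.382 = 1.10.

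**The case against.** The plan's declared aim is confounder control, and a variable the app changes is not a confounder. Section 7.6 also gives the intermediate measures another role, as things to be affected. On that reading the plan is under-specified and does not propose adjusting for mediators. This stands, and it makes the harm to β3 conditional. It does not remove the commitment to unnamed post-randomisation covariates.

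A reader might go further and infer that the app's targets will be covariates, because most repeated measures in Table 6 are outcomes and because Section 4.6 plans to relate risk behaviour to changes in substance use, stigma and victimization. The documents do not support this. Table 6 is a list of outcome measures, not a covariate pool, and Section 4.6 describes triangulation with the interviews, not the GLMM.

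A reader might also infer that a distorted ratio will size the future trial. That is not shown. Section 7.6 names Cohen's d and Hedges' g with no covariate adjustment stated, and its RR of 0.55 is not tied to any model.

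On the partner factors, the analysis is already described as secondary and sensitivity-only, partner reports are acknowledged to be unreliable, Section 7.3.2 plans to examine differential attrition, and the two cited method papers concern direct and indirect effects. All true, but step 3 still states a wrong inference. Nor would it be right to relabel the steps as a mediation analysis, since that presumes one of the explanations they cannot separate.

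Finally, the illustrations use a conditional Poisson fit and a GEE, not the planned random-intercept model, and every mediated share is assumed. The direction rests on the algebra; the sizes are illustrative.

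**Conclusion.** The point holds in two parts and should be fixed.

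First, the plan commits the model for all outcomes to unnamed post-randomisation covariates while reading β3 as the intervention's impact. Randomisation makes that adjustment unnecessary for confounding. If any covariate used is affected by the app, exp(β3) is no longer the total effect; if none is, there is no distortion. The size cannot be computed from the documents, and 0.64, 0.74 and 0.86 against 0.55 hold only for the assumed shares. The documents do not show that β3 will be biased.

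Second, step 3 of the sensitivity analysis is wrong as written. This part does not depend on assumed numbers: its two conditions do not establish bias in the main estimate.

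One limit applies to the remedy. A reader might take a baseline-only model to guarantee the 3-month total effect. It does not, because Table 7 assumes a constant effect from 3 to 6 months. Let b and c be the intervention arm's log effects at 3 and 6 months, and b the delayed arm's at 6 months. The arm difference over the waves is 0, b, c−b, and the INT difference is 0, 1, 0. With equal weights and wave indicators, β3 = b − (c−b)/2 = b + (b−c)/2, which equals b only if c = b. That is a separate matter.

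**What to change.** In the Data Analysis paragraph of Section 7.6:
- Take the primary β3 from a model with Arm, W, INT, the random intercept and a named, pre-specified list of baseline covariates only.
- Confine wave-level covariates to a supplementary model, labelled as such, with its variables named.
- State that any RR carried to future-trial planning comes from the model without wave-level covariates.

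In the Sensitivity Analysis paragraph:
- Delete the statement that the main estimate is biased and will be corrected.
- Report steps 1 to 3 as an exploratory analysis of partner factors, with a stated estimator and no claim that it replaces the primary estimate.
- Define the step 2 outcome as anal and/or vaginal acts, to match the primary outcome.

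This is wording only and needs no new data. The downside is any precision that wave-level covariates would have added. In the illustration the SE of β3 was about 0% to 10% larger without them, under assumed covariate strengths. The supplementary model would still report the adjusted result.

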Overview. We will conduct a 6-month randomized controlled pilot study with 80 YTM. The goals of the pilot study are to: a) Gain direct feedback from participants about whether and to what degree the MyPEEPS Mobile App worked as intended; b) Assess the acceptability of MyPEEPS Mobile dosing and content for YTM; and c) Observe the flow of procedures, including assessment at baseline, retention efforts, data management, and follow-up assessments. The recruitment plan, screening, and consent/assent processes are described in the Protection of Human Subjects and Clinical Trials Information sections. Our **primary outcome for this study will be:** change in number of condomless receptive anal or vaginal sex acts with sex partners assigned male at birth. **Sampling Approach to Successfully Enroll YTM in this Project.** We will recruit 80 participants from an online national sample and ensure that at least half of our sample is from racial/ethnic minority groups. Using active and passive recruitment methods, the on-site project coordinators will oversee and participate in recruitment efforts. The study staff hired for this project, on-site coordinator, and the peer-to-peer networking efforts will be used to recruit study participants. Our pilot study will comprise a convenience sample through active online recruitment through Instagram, Twitter, Snapchat, and Facebook advertisements. We will use psychographic targeting (in-depth, publicly available consumer data such as interests, city) to advertise only to potentially eligible individuals. We have successfully used this approach to recruit our sample of YMSM in the MyPEEPS project. Through our advertisements, and as previously mentioned, we have screened

>800 YTM who would be eligible for the proposed MyPEEPS study, *and we will plan to recruit them as well as others into the proposed study. We are confident in our ability to enroll the proposed target sample.*

Sample Size and Power Calculation. This study plan is to enroll 80 participants with 1:1 random assignment to the intervention arm and the control arm (i.e., 40 in each arm). Compared to a large-scale randomized trial, we do not expect that this pilot trial will have power to detect many of the

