[Figure 2. Assessment Time Points and Intervention Delivery for Each Study Arm](#)

The delayed intervention design is essentially a cross-over design in which data are collected in parallel from both study arms through the primary endpoint - 3-months post-randomization ([Figure 2](#)). The arms are then crossed over, which has multiple benefits, including: 1) for ethical reasons per our experience with HIV prevention interventions with transgender populations, the delayed intervention group receives the potential benefit of the

intervention at the point of cross-over; 2) at the 6-month follow-up, it provides for a test of the durability of the intervention effect in the intervention group (i.e., 3-months post-intervention, pre-post); 3) it provides an additional secondary test of the intervention effect in the delayed intervention arm (pre-post); and 4) it provides additional time points (and power) in the intervention group to test moderators of the trajectory of sexual risk over time. We successfully used this study design in an NIH-funded R34 study(61).

MyPEEPS avatars represent “regular guys” like the study participants who will walk the participants through the curriculum. Following the selection of an avatar, the study participant will navigate through each of the study activities. Participants do not need to complete an activity in a single sitting but can stop and come back to complete the activities at any time during the time frame before the 3-month follow-up. Study staff will have access to a dashboard to monitor module completion. In addition, participants will receive weekly text messages and/or e-mails (participants will select) to remind them to complete the MyPEEPS module. If 2 weeks have passed and a participant has not completed any modules, then the app will send out notification reminders to remind them to complete their modules.

4.6 Specific Aim 3 Procedures.

Overview. Post-intervention, we will conduct individual, in-depth, semi-structured interviews with participants who completed the intervention.

Sample. We will purposively select participants to represent a diverse set of experiences (e.g., participants who completed App Use, high vs. low sexual activity). Although we will continue to recruit participants until reaching thematic saturation, we anticipate conducting about 20 interviews

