7.1 DATA MANGEMENT, SECURITY & ANALYSIS

7.2 Power Considerations and Sample Size Calculation (Aim2)

Sample Size and Power Calculation. The study plan is to enroll 80 participants with 1:1 random assignment to the intervention arm and the control arm (i.e., 40 in each arm). Compared to a large- scale randomized trial, we do not expect that this pilot trial will have power to detect many of the effects that would be of scientific or policy significance. This is consistent with the aims of this pilot grant mechanism, where budgetary limitations necessitate small sample sizes. Group means on continuous variables typically begin to stabilize by 20-30 participants. Thus, a sample size of 40 participants per group should provide relatively stable group means for the intervention and control conditions, even with some sample attrition.

Study Design. Participants in the intervention group will be able to access the MyPEEPS intervention from baseline until the end of month 3, and the control arm (delayed intervention) will have access to the MyPEEPS App from months 4-6.

Overview of Data Collection Time Points. We will conduct simultaneous assessments for both study arms at baseline, 3 months, and 6 months. We will also collect an immediate post-intervention assessment for the delayed intervention arm. The delayed intervention design is essentially a cross-over design in which data are collected in parallel from both study arms through the primary endpoint - 3 months post-randomization. The arms are then crossed over, which has multiple benefits, including: 1) for ethical reasons per our experience with transgender populations, the delayed intervention group receives the potential benefit of the intervention at the point of cross-over; 2) at the 6-month follow-up, it provides for a test of the durability of the intervention effect in the intervention group (i.e., 3 months post-intervention, pre-post); 3) it provides an additional secondary test of the intervention effect in the delayed intervention arm (pre-post); and 4) it provides additional time points (and power) in the intervention group, to test moderators of the trajectory of sexual risk over time.

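### The primary endpoint is set at 3 months, but the one model described for the primary count lets month-6 data from both arms into the intervention coefficient, under an equal-effect assumption the readable text does not state

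*Combined protocol and SAP*

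**What the plan says.** - **Time point.** Section 4.5 says that "data are collected in parallel from both study arms through the primary endpoint - 3-months post-randomization"; section 7.2 repeats this. The arms are then crossed over.
- **Further tests.** Among the benefits of the crossover, section 4.5 lists that "at the 6-month follow-up, it provides for a test of the durability of the intervention effect in the intervention group". It lists the delayed arm's own pre-post change as a further test and calls that one secondary.
- **Outcome.** The overview in section 4.5 defines the primary outcome as "change in number of condomless receptive anal or vaginal sex acts with sex partners assigned male at birth". The definition itself carries no time point.
- **Model.** Section 7.6 states: "We propose the following generalized linear mixed model (GLMM) to analyze all outcomes". The waves are baseline, 3 and 6 months. Table 7 codes INT as 0, 1, 1 in the intervention arm and 0, 0, 1 in the delayed arm, and W as 0, 1, 2. The coefficient of INT, β3, "is the mean value change for the outcome variables between pre- and post-intervention and measures the impact of the intervention".
- **Purpose.** Section 7.6 says that the study is not powered for efficacy, and that the primary outcome will be used to estimate an effect size for a larger trial.

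**The concern.** The protocol reserves the month-6 data for two further questions, yet the same data enter the coefficient that is called the intervention's impact. Because INT is 1 in both arms at month 6, that visit does not simply add follow-up to the intervention effect. It works as a second point at which the arms are assumed to be alike. Planning a durability test means that the later effect is an open question, whereas the pooled coefficient treats it as settled.

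The direction is easy to misjudge. One would expect an effect that fades after month 3 to dilute a pooled estimate; here it inflates it. What is at stake is the rate ratio reported for the primary outcome and, if that is the figure carried forward, the planning of the R01.

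**Working it through.** The plan gives no figure for this contrast, so there is none to reproduce. From the documents come the Table 7 codes, 40 participants per arm, and the rate ratio 0.55 that section 7.6 uses in its R01 power statement. Trajectories, time trends, dispersions, baseline means, within-person correlations and month-by-month retention are assumptions; the documents say only that at least 80% will be retained.

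**1. Weights.** Take intercept, Arm, W and INT as main effects with a random intercept and 40 per arm. On the link scale the generalised least squares weights of β3 on months 0, 3, 6 are:

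| Arm | Month 0 | Month 3 | Month 6 |
|---|---|---|---|
| Intervention | -0.5 | 1 | -0.5 |
| Delayed | 0.5 | -1 | 0.5 |

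They are the same for W linear or categorical and for within-person correlations of 0.3, 0.5 and 0.8. Let D be the between-arm log ratio (intervention minus delayed). Then

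β3 = D3 - (D0 + D6)/2.

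Randomisation makes D0 zero on average. D6 is zero only if both arms carry the same effect at month 6.

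**2. Size on the link scale, flat trend, D3 = ln 0.55.**
- Constant and equal effect: D6 = 0, so exp(β3) = 0.55.
- Gone by month 6 in the intervention arm, full effect in the delayed arm: D6 = -ln 0.55, so exp(β3) = 0.55^1.5 = 0.41.
- Builds to 0.40: D6 = ln(0.40/0.55), so exp(β3) = 0.55 × √(0.55/0.40) = 0.64.
- Delayed arm gets half the effect: D6 = 0.5 × ln 0.55, so exp(β3) = 0.55^0.75 = 0.64.

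**3. Count models.** With a log link the weights depend on the fitted means. Poisson and negative binomial fits to expected cell means (baseline mean 5, dispersion 0.5 to 2, complete data), taken with step 2, give 0.41-0.45 if the effect has gone, 0.59-0.64 if it builds to 0.40, and 0.62-0.64 if the delayed arm gets half. A contrast restricted to month 3 returns 0.55 in all of these.

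**4. Size against sampling error.** Random-intercept negative binomial models were simulated at N=80, with assumed retention of 90% and 80% at months 3 and 6, a flat trend, and two assumed parameter sets. If the effect has gone by month 6, β3 shifts by 0.25-0.27 log units, which is 0.63-0.83 of its sampling SD. If the effect builds to 0.40, the shift is 0.10-0.12 log units (0.28-0.32 SD).

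**5. Form of W.** Suppose counts fall once, by 40%, after baseline in both arms.
- Constant effect of 0.55: linear W returns 0.57 (negative binomial, dispersion 1) to 0.60 (Poisson); categorical W returns 0.55.
- No effect, retention at months 3 and 6 of 95%/90% in the intervention arm and 80%/70% in the delayed arm: linear W returns about 0.96, or about 1.04 with the arms exchanged; categorical W returns 1.00.

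**6. Precision if the effect really is constant.** In common units the variance is 1.5(1 - ρ) for the pooled coefficient and 1 - ρ² for a baseline-adjusted 3-month comparison, where ρ is the within-person correlation. The ratio is (1 + ρ)/1.5, which is 1.00 at ρ = 0.5 and 1.20 at ρ = 0.8.

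**The case against.** The strongest reply is that the model equation is lost, so nobody working from this text can be sure what β3 is. That stands. With categorical W and an Arm-by-INT term, β3 would be D3 - D0, exactly the baseline-adjusted 3-month contrast. The surrounding text names no such interaction, but that is weak evidence when the display itself is missing. A reader might therefore infer that the plan's primary analysis is wrong as written, or that it fails to say whether W is linear or categorical. The documents support neither: the equation may settle both, so the request is to confirm and state.

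A single intervention indicator is also legitimate when the effect is constant and equal in the two arms, and it is more precise when ρ exceeds 0.5. That is true, but the gain rests on an assumption that the readable text does not give.

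Finally, this is a pilot with no efficacy power. The planned durability test would give some information on waning, and section 7.6 also plans Cohen's d and Hedges' g between arms. This limits the consequence. It does not remove the mismatch, because the primary count would still be summarised by a coefficient tied to a different time structure from the declared endpoint.

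**Conclusion.** The mismatch between a 3-month primary endpoint and an indicator that also draws on month 6 can be read directly from section 4.5, section 7.2 and Table 7. Its numerical effect depends on the main-effects reading of the lost equation. On that reading, β3 equals the 3-month effect only if the arms do not differ at month 6 and the wave term fits the time trend. In practice the first condition means no waning or building in the intervention arm and the same response in the delayed arm. For a true 0.55 the reported ratio could lie anywhere from about 0.41 to about 0.64 under the assumed flat-trend scenarios.

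Two stronger conclusions are not supported. A reader might infer a materially raised false-positive risk. With no effect and categorical W, the coefficient is centred on a ratio of 1.00; only linear W combined with a non-linear trend and unequal retention moves it, and in the example only to about 0.96 or 1.04. A reader might also infer that the R01 would be mis-sized by a calculable factor. The documents do not say which estimate, or which time point, feeds that calculation.

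This is a cheap improvement: the shift is below one standard error at N=80, and it bears on an effect size that the plan intends to carry forward.

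**What to change.** - **Primary estimate.** Make it the 3-month between-arm rate ratio with its 95% confidence interval. Obtain it either from a mixed model with categorical visit, separate arm-by-visit terms at 3 and 6 months and a common baseline, or from negative binomial regression of the 3-month count on arm and baseline count.
- **Secondary contrasts.** Report 6-month durability in the intervention arm and the delayed arm's pre-post change separately, each with its own model term.
- **Pooled INT model.** Keep it as secondary, confirm that W is categorical, and write down the assumption of equal effects in the two arms at month 6.
- **R01 planning.** State which estimate and which time point will be used.

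The cost is SAP wording and a standard model on the same data. If the effect really is constant, the variance changes by the factor (1 + ρ)/1.5: none at a within-person correlation of 0.5, 20% more at 0.8, and a gain below 0.5. The change should be made before outcome data are examined.
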